1.7 Rationale for Double-Blinding

This study has been designed to be double-blinded despite having an objectively ascertained primary endpoint (survival) for the following reasons:

- There will be no study defections due to randomization disappointment (so subjects randomized to placebo will not quit the study).
- There will be no difference in use of post-treatment anti-cancer therapies or concomitant therapies due to knowing the intervention being delivered.
- There will be no difference in the interpretation of biomarkers or lab tests due to knowing the intervention being delivered.
- The between-arm comparison of adverse events will not be corrupted by knowing the intervention being delivered.

2.0 NAME AND DESCRIPTION OF STUDY AGENTS

2.1 Formulation, Packaging, and Labeling

The PROSTVAC-V/F study vaccines, including placebo, are manufactured at [REDACTED] in compliance with current good manufacturing practices (cGMPs). The formulations do not contain adjuvants or preservatives. [REDACTED]

[REDACTED] the vials are sealed with rubber injection stoppers and plastic/aluminum flip-caps, and a label is affixed to the vial. PROSTVAC-V/F study vaccine vials are then packaged in 6-vial cartons with an outer carton label.

GM-CSF (Leukine[®]: 250 µg, lyophilized) will be purchased from licensed, US pharmacy wholesalers. Lyophilized GM-CSF is reconstituted with 1.0 mL bacteriostatic water for injection. GM-CSF vials will not be relabeled, and will be packaged in 5-vial cartons with an outer carton label.

GM-CSF placebo is bacteriostatic sodium chloride for injection and will be purchased from licensed, US pharmacy wholesalers. GM-CSF placebo vials will not be relabeled, and will be packaged in 25-vial trays with a label.

Examples of carton and vial labels are included in [Appendix 14.10](#).

2.2 Investigational Drug Product (PROSTVAC-V/F)

PROSTVAC-V/F is comprised of two components. PROSTVAC-V is a replication-competent vaccinia virus which has been engineered to encode the sequences for a modified human prostate-specific antigen (PSA) and a triad of co-stimulatory molecules (TRICOM). PROSTVAC-F is a fowlpox virus which does not replicate in human cells and has been engineered to encode the same sequences present in PROSTVAC-V. A full description of the PROSTVAC-V/F product and PROSTVAC-V/F pre-clinical and clinical support are contained in the Investigator's Brochure.

Study vaccine for this trial contains no preservatives or adjuvants and is supplied in single-dose 2 ml clear, borosilicate glass injection vials with rubber injection stoppers covered by a plastic-aluminum flip cap.

Active Ingredient: PROSTVAC-V: PROSTVAC-V-PSA-TRICOM in aqueous solution for injection
PROSTVAC-F: PROSTVAC-F-PSA-TRICOM in aqueous solution for injection

Product Description: PROSTVAC-V/F is comprised of two recombinant pox viruses: a recombinant vaccinia virus (PROSTVAC-V) and a recombinant fowlpox virus (PROSTVAC-F). [REDACTED]

Dose: 0.5 ml containing at least 2×10^8 Infectious Units (Inf.U) PROSTVAC-V

0.5 ml containing at least 1×10^9 Inf.U PROSTVAC-F

Route of Administration: Subcutaneous injection

Storage*: -70°C or below

There is no pre-treatment regimen for PROSTVAC-V/F.

* Storage conditions and stability claims for the final PROSTVAC-V/F product are based on long-term manufacturing experience with PROSTVAC-V/F by Therion, the initial manufacturer. The stability data for PROSTVAC-V/F shows virus titer stability for four years when stored at -80°C ($\pm 10^{\circ}\text{C}$).

Regimen of Administration: Doses of PROSTVAC-V/F or placebo will be drawn into labeled syringes by an independent, unblinded research pharmacist or designee for use by the clinic staff. PROSTVAC-V will be administered by the study staff once by sc injection on one side (upper arm or upper outer thigh) during Week 1. PROSTVAC-F will be administered by the study staff six times by sc injection during Weeks 3, 5, 9, 13, 17, and 21. Vaccination with PROSTVAC-F will begin on one side (upper arm or upper outer thigh), and subsequent immunization sites should be rotated to the opposite side and/or limb if possible.

2.3 GM-CSF

GM-CSF (Leukine[®]: 250 μg , lyophilized) will be purchased from licensed, US pharmacy wholesalers and labeled appropriately for the study. Lyophilized GM-CSF will be reconstituted using 1.0 ml of room temperature bacteriostatic water for injection (USP-grade or equivalent). Product reconstituted with bacteriostatic water for injection is stable for 20 days if stored between 2 and 8°C in the original vial. See product label for information related to product description and formulation. Doses of GM-CSF of 100 μg each will be drawn into labeled syringes by an independent, unblinded research pharmacist or designee for use by the clinic staff or by individual subjects for home injection (subjects enrolled in France must return to the clinic to receive GM-CSF injections).

Dose: 0.40 ml (100 μg) GM-CSF

Route of administration: Subcutaneous injection

Storage: 2 - 8°C (lyophilized and reconstituted); Up to 4 days at 2 - 8°C when in syringes

Regimen of administration: GM-CSF will be injected sc by the study staff on the day of vaccine or placebo administration and for the subsequent 3 days, within approximately 5 mm of the injection site by the study staff, the subject, or subject's caregiver (subjects enrolled in France must return to the clinic to receive GM-CSF injections).

2.4 PROSTVAC-V/F Placebo: Empty fowlpox vector

The PROSTVAC-V/F placebo will be provided in blinded vials matched to active product. The same placebo will be used for both vaccinia and fowlpox PROSTVAC-V/F components.

Dose:	0.5 ml containing at least 1×10^9 Inf.U
Route of administration:	Subcutaneous injection
Storage:	-70°C or below
Regimen of administration:	
PROSTVAC-V placebo will be administered once by sc injection by the study staff in the upper arm or upper outer thigh during Week 1.
 
PROSTVAC-F placebo will be administered by the study staff six times by sc injection during Weeks 3, 5, 9, 13, 17, and 21. Vaccination with PROSTVAC-F placebo will begin on one side (upper arm or upper outer thigh), and subsequent immunization sites should be rotated to the opposite side and/or limb if possible.

2.5 GM-CSF Placebo

GM-CSF placebo will consist of USP-grade or equivalent bacteriostatic sodium chloride (saline) for injection. Doses of GM-CSF placebo will be drawn into labeled syringes by an independent, unblinded research pharmacist or designee for use by the clinic staff or by individual subjects for home injection (subjects enrolled in France must return to the clinic to receive GM-CSF placebo injections).

Dose:	0.40 ml injection of bacteriostatic sodium chloride (saline) for injection
Route of administration:	Subcutaneous injection
Storage:	Room temperature when in vials; Up to 4 days at $2-8^{\circ}\text{C}$ when in syringes
Regimen of administration:	GM-CSF placebo will be administered sc on the day of PROSTVAC-V/F or PROSTVAC-V/F placebo vaccination by the study staff and for the subsequent 3 days, within approximately 5 mm of the PROSTVAC-V/F or PROSTVAC-V/F placebo vaccination site by the study staff, the subject, or the subject's caregiver (subjects enrolled in France must return to the clinic to receive GM-CSF placebo injections).

3.0 STUDY OBJECTIVES AND ENDPOINTS

3.1 Study Objectives

3.1.1 Primary Efficacy Objective

To ascertain whether the survival of subjects randomized to Arm V+G (PROSTVAC-V/F plus GM-CSF) or to Arm V (PROSTVAC-V/F) is superior to that from subjects randomized to Arm P (placebo control).

3.1.2 Secondary Efficacy Objective

To ascertain whether a greater proportion of subjects randomized to Arm V+G or to Arm V remain event-free at six months (or early termination) as compared to the subjects randomized to Arm P.

3.1.2.1 Definition of Event (To be Used in Secondary Endpoint)

Progression events will be defined as:

- Radiographic progression
 - Two new lesions on bone scan, new metastases on CT scans*, or an increase size of nodal lesions per RECIST 1.1.
- Pain progression
 - Introduction of scheduled opioid narcotics for cancer-related pain control.
- Initiation of chemotherapy
- Death

* For subjects with allergies to contrast agents, MRIs for abdomen and pelvis may be performed. Only in cases where MRI is unavailable may a non-contrast CT be performed. For subjects enrolled in Germany, MRI must be used as the primary imaging modality.

Radiographic progression will be assessed by bone scan at 3 and 6 months, and by CT scan (or MRI for subjects in Germany) at 6 months (and at the time of progression, or any time during the treatment period if clinically indicated). For secondary endpoint analysis, baseline scans and 6 month scans (or early termination scans) will be compared by central radiology review. Bone scan and CT (or MRI for subjects in Germany) data will be archived up to five years past the end of the trial.

In addition, for an exploratory endpoint, we will assess radiological progression at 12 months (6 months post End-of-Treatment visit) by comparison with the 6 month scans (from End-of-Treatment visit or early termination). This will attempt to define effects on secondary progression, and characterize delayed effects of investigational vaccine therapy.

3.1.3 Safety Objective

To further characterize the safety and tolerability of PROSTVAC-V/F immunotherapy, characterize type and number of AEs compared to placebo.

3.1.4 Exploratory Objectives

To model secondary radiological disease progression over the first year of study participation.

To ascertain whether a greater proportion of subjects randomized to either Arm V+G or Arm V remain event-free (radiological progression) six months post End-of-Treatment visit (using scans at End-of-Treatment visit as a new baseline), as compared to the subjects randomized to Arm P. This analysis will include all subjects, and separately the HLA-A2-expressing subgroup.

To assess the role of post-treatment anti-cancer therapies as an alternative explanation for observed survival differences.

To ascertain whether the survival of HLA-A2-expressing subjects randomized to Arm V+G, or Arm V is superior to that from HLA-A2-expressing-subjects randomized to Arm P.

To ascertain whether a greater proportion of HLA-A2 expressing subjects randomized to Arm V+G or to Arm V remain event-free at six months as compared to the HLA-A2 expressing subjects randomized to Arm P.

To compare arms with respect to immune response to immunizing antigen (PSA), as well as to non-vaccine containing prostate antigens, and tumor-associated antigens, and assess whether immune responses are prognostic and/or predictive.

To evaluate for baseline biomarkers which are prognostic and/or predictive of long term survival outcome.

To compare arms with respect to vaccine effects on circulating tumor cell (CTC) levels (US sites only).

3.2 Study Endpoints

3.2.1 Primary Efficacy Endpoint

The primary efficacy endpoint for the trial is overall survival.

3.2.2 Secondary Efficacy Endpoint

The secondary efficacy endpoint for the study is the proportion of event-free subjects (radiological progression, pain progression, chemotherapy initiation, or death) at six months (or early termination) compared to placebo.

4.0 INVESTIGATIONAL PLAN

4.1 Study Design

BNIT-PRV-301 is a randomized, placebo-controlled, multi-center, multi-country, Phase 3 efficacy trial of PROSTVAC-V/F in men with asymptomatic or minimally symptomatic, metastatic, castration-resistant prostate cancer. Subjects will be randomized with equal probability (1:1:1) to one of three double-blind arms; two investigational arms (Arm V+G; Arm V), and a control arm (Arm P). The study will consist of three periods: a Screening phase, followed by Treatment, and subsequently Long-Term Follow-Up (LTFU) phases.

The intended intervention in Arm V+G is PROSTVAC-V/F plus GM-CSF; Arm V intended intervention is PROSTVAC-V/F plus GM-CSF placebo, whereas the intended intervention in Arm P is vaccine placebo plus GM-CSF placebo. The trial interventions will consist of a single sc immunization of PROSTVAC-V or placebo in Week 1, followed by six PROSTVAC-F or placebo immunizations administered in Weeks 3, 5, 9, 13, 17, and 21. Each immunization will be accompanied by administration of sc GM-CSF or placebo on the day of immunization and for the subsequent three days (sc injection within 5 mm of the original PROSTVAC V/F or placebo injection site). The Treatment phase of this trial lasts for five months and is followed by an End-of-Treatment visit at Week 25. During the Treatment phase, subjects will continue to be treated with vaccination therapy or placebo through PSA and/or radiological progression.

Following the completion of the Treatment phase (after the last dose of PROSTVAC-V/F \pm GM-CSF or placebo or early termination of treatment) of the trial, all subjects will automatically enter the LTFU phase with study visits occurring every six months. During LTFU subjects will receive standard-of-care treatment as determined by the Principal Investigator or treating physician. The appropriate timing and the nature of any subsequent treatment will be at the discretion of the Principal Investigator or treating physician. All treatments for mCRPC subsequent to the Treatment phase of the trial will be documented in the CRF. This comprehensive data will be collected until study closure, death, or until a subject withdraws from the study.

The primary endpoint for the study is overall survival. All subjects will be followed for 12 months after the required number of 534 events for each between-arm comparison is realized.

4.2 Sample Size

This study will evaluate approximately 1,200 subjects (400 subjects/arm) with a 1:1:1 randomization of PROSTVAC-V/F plus or minus GM-CSF versus placebo control plus GM-CSF placebo.

4.3 Selection of Study Population

All subjects will be men \geq 18 years old with asymptomatic or minimally symptomatic, metastatic CRPC. Subjects will have progressive disease following androgen suppression or complete blockade therapy, or surgical castration; and will be chemotherapy naïve for metastatic prostate cancer. Subjects must be

vaccinia experienced (previous smallpox vaccination). Subjects must have a castrate testosterone level of <50 ng/dl at study entry.

For subjects on anti-androgens, a 6-week washout is required (4 weeks if on flutamide).

Prospective subjects may be screened from hospital or clinic records or databases, or may be new patients. At the discretion of the institution, subjects may be recruited by advertisements, on-line, in newsletters or journals, flyers, or on radio provided the content and distribution is approved by BNI and by the IRB/EC prior to use or release. BNI will list the study on the government website, www.clinicaltrials.gov.

4.4 Targeted Enrollment of Minorities

Attempts will be made (in the US) to specifically enroll minority subjects up to the level of representation in the general US population. Cities with high minority populations will be specifically targeted for center recruitment, as will study centers serving primarily minority populations; e.g., Historically Black Colleges and Universities. Attempts will be made to tailor advertising and recruitment tools to minority groups and to enlist the help of subject advocacy groups in high minority population centers.

4.5 Method of Assigning Subjects to Treatment Groups

This study is double-blind and placebo-controlled. Enrollment will be randomized with equal probability to each of three double-blinded arms: two investigational arms (Arm V+G or Arm V) and a control arm (Arm P). The intended interventions associated with the arms are: active treatment with PROSTVAC-V/F + GM-CSF (Arm V+G); PROSTVAC-V/F + GM-CSF placebo (Arm V); or placebo control (Arm P). Block randomization will be used to randomly assign subjects in a 1:1:1 manner. Randomization will be stratified according to the following two factors, PSA (equal and above or below 50 ng/ml) and LDH (equal and above or below 200 U/mL).

4.6 Inclusion Criteria

Eligible subjects must meet all the following criteria (there will be no exemptions for Inclusion/Exclusion criteria):

1. Signed Informed Consent.
2. Men, ≥ 18 years of age with documented asymptomatic or minimally symptomatic metastatic castration-resistant prostate cancer.
3. Castrate testosterone level < 50 ng/dl.
4. Documented progressive disease post-surgical castration or during androgen suppression therapy, or during complete androgen blockade therapy and withdrawal. Documented by either criterion a (Radiological progression), **OR** criterion b (PSA progression).

- a. Radiological progression defined as any new/enlarging bone metastases or new/enlarging lymph node disease, consistent with prostate cancer.

OR

- b. PSA progression defined by sequence of rising values separated by > 1 week (2 separate increasing values) over a threshold minimum of 2.0 ng/ml. (PCWG2 PSA eligibility criteria).
5. Chemotherapy naïve. No prior chemotherapy for metastatic prostate cancer. Neo-adjuvant or adjuvant chemotherapy for primary prostate cancer is permissible if >3 years prior.
 6. Vaccinia-experienced (previous smallpox vaccination).
 7. ECOG Performance Score of 0 or 1.
 8. Life expectancy \geq 1 year.
 9. Bone Marrow function:
 - Absolute neutrophil count \geq 1,500/mm³
 - Hemoglobin \geq 10 g/dL
 - Platelet count \geq 100,000/mm³
 10. Hepatic Function:
 - AST and ALT \leq 2.5 times upper limit of normal (ULN)
 - Bilirubin \leq 1.5 times ULN
 11. Renal Function:
 - Creatinine \leq 2.0 times ULN
 12. Currently using a GnRH agonist or antagonist (unless surgically castrated).

4.7 Exclusion Criteria

Subjects with any of the following will be excluded from enrollment:

1. Cancer-related pain requiring scheduled opioid narcotics for control (as needed, \leq 2x per week is allowed).
2. Metastasis to organ systems other than lymph nodes and/or bone.
3. LDH \geq 2 times ULN.
4. Alkaline phosphatase \geq 2 times ULN.

5. Estimated PSA doubling time of <1 month as established within 6 months of the anticipated first dose of vaccine or placebo. A minimum of 3 PSA level determinations, at least 2 weeks apart (over a 6 month time-period), are required for assessment.
6. Concurrent or prior Provenge (sipuleucel-T) immunotherapy for prostate cancer.
7. Receipt of an investigational agent within 30 days (or 60 days for an antibody-based therapy) of the first planned dose of PROSTVAC-V/F. There is no exclusion to previous experimental therapy provided dosing/treatment is completed at least 30 days prior to the first planned dose of vaccine unless otherwise noted.
8. History of prior malignancies other than prostate cancer within the past 3 years, excluding successfully resected basal or squamous cell carcinoma of the skin.
9. Congestive heart failure (NYHA Class II, III, or IV), unstable angina, ventricular or hemodynamically significant atrial arrhythmia, or cardiovascular disease such as stroke or myocardial infarction (current or within the past 6 months).
10. Confirmed positive for HIV, hepatitis B, and /or hepatitis C.
11. Prior solid organ or bone marrow transplant.
12. Immunodeficiency or splenectomy.
13. Chronic immunosuppressive therapy within 30 days of screening.
14. Inflammatory eye disease requiring steroid treatment.
15. Chronic administration (defined as daily or every other day for continued use > 14 days) of systemic corticosteroids within 28 days of the first planned dose of PROSTVAC-V/F. Use of inhaled steroids, nasal sprays, and topical creams for small body areas is allowed.
16. History of or active autoimmune disease (e.g., autoimmune neutropenia, thrombocytopenia, or hemolytic anemia, systemic lupus erythematosus, Sjogren's syndrome, scleroderma, myasthenia gravis, Goodpasture's syndrome, Addison's disease, Hashimoto's thyroiditis, or Graves disease). Persons with vitiligo are not excluded. Diabetics are not excluded if the condition is well controlled.
17. Known allergy to eggs, egg products, aminoglycoside antibiotics (for example, gentamicin or tobramycin), or GM-CSF. Subjects with a known or suspected allergy to radiological contrast agents are eligible, but this must be noted in the subject's medical history and in the chart notes.

18. History of atopic dermatitis or active skin condition (acute, chronic, exfoliative) that disrupts the epidermis.
19. Previous adverse reactions to smallpox vaccination.
20. Unable to avoid close contact or household contact with the following high-risk individuals for three to four weeks after the Day 1 vaccination or until the vaccination site heals completely: (a) children < 3 years of age, (b) pregnant or nursing women, (c) individuals with prior or concurrent extensive eczema or other eczematoid skin disorders, or (d) immunocompromised individuals, such as those with HIV.
21. Significant medical abnormality (defined as a pre-existing condition AE/condition \geq Grade 3 according to NCI CTCAE v 4.0 and any condition which, in the opinion of the investigator, would prevent full participation in this trial (including the Long-Term Follow-Up), or would interfere with the evaluation of the trial endpoints.
22. Study personnel.

5.0 SAFETY MONITORING

5.1 Data Monitoring Committee (DMC)

An independent Data Monitoring Committee will be established to ensure subject safety, to consider subject risks against the potential for meeting trial objectives, and to provide recommendations to BNI with respect to the conduct and analysis of the trial. The DMC will operate independently of BNI with the exception of the administration of compensation to the DMC members for DMC-related activities and non-voting activities such as clinical trial conduct updates. The voting members of the DMC will be a multi-disciplinary group that may include representative physicians who treat the type of subjects entered onto this trial; one or more individuals with statistical expertise; and if appropriate, one or more biological scientists. The DMC will meet either by phone or in person and will be provided with all available pertinent subject data in a manner specified in the approved Charter. An Executive Summary of Committee recommendations generated at each meeting will be forwarded to all IRBs/ECs as requested or required. Minutes of the closed sessions will be held in confidence by the DMC or its designee until the official close of the trial. The exact constitution and conduct of the DMC will be ultimately governed by the approved Charter. A vital status sweep will be performed in conjunction with each DMC meeting to ensure the most current data is being reviewed.

5.2 Dose-limiting Toxicities and Trial Stopping Rules

5.2.1 Dose-limiting Toxicities

For the purposes of this trial, a dose-limiting toxicity (DLT) is defined as any anaphylactic reaction, a full-thickness ulceration/necrosis, or any AE \geq Grade 3 definitely related to study drug with the following exceptions:

- Local injection site reactions lasting < 72 hours: pain, redness, swelling, induration, or pruritus
- Systemic injection reactions lasting < 72 hours: fever; myalgia, headache, nausea, fatigue

Study drug should be discontinued for the subject in the case of a definitely related anaphylactic reaction or full-thickness ulceration/necrosis. Re-exposure to study drug after development of other related AE \geq Grade 3 should only occur if the event resolved or is reduced to grade 1 toxicity.

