5.2.2 Trial Stopping Rules

In the event of a death definitely related to study drug within 24 hours of vaccination or ≥ 3 definitely related SAEs (per 20 patients) at any time after receiving study drug during the treatment period, dosing will halt immediately and the DMC will be consulted. All data will be reviewed prior to any further dosing, and dosing will not continue until the DMC agrees that it is safe to continue. At the discretion of the DMC, the FDA or other Health Regulatory Agencies may be consulted. The decision to permanently halt the trial may only be made by BNI Executive Committee.

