5.4 Removal of Subjects from Therapy or Assessment

Subjects may withdraw consent for participation in the study at any time without prejudice. Additionally, the investigator may withdraw a subject if, in his/her clinical judgment, it is in the best interest of the subject or if the subject cannot or will not comply with the protocol. Wherever possible, the End-of-Study tests and evaluations listed in [Section 7.4](#) should be carried out at the time the subject withdraws or whenever the Investigator feels that the subject will be unable to make any further visits.

If a subject fails to return for the necessary visits or discontinues prematurely from the study, a genuine effort must be made to determine the reason why. If the subject or his designated contact is unreachable by telephone, the minimum of a registered letter should be sent requesting that contact be made with the Investigator (or designee) to report survival information. Every attempt possible to obtain follow-up blood samples for safety and immune monitoring should be made. Request for an autopsy, autopsy report and death certificate when/if the subject expires while on trial should be pursued.

BNI may discontinue individual subjects, study arms, individual study centers, or the entire study at any time provided sufficient time is given to ensure subject safety.

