6.7 Dose Reductions and Contraindications for PROSTVAC-V/F

There are no dose reductions for this study. Subjects who experience intolerable reactions will be discontinued from treatment but will remain on study and be followed for safety, immune status, and survival per protocol. PROSTVAC-V/F will be discontinued as defined in [Section 5.4](#). Subjects discontinued from further vaccination should remain on study and continue to be followed for safety, immune status, and survival per protocol.

For acute illnesses (fever, infectious disease, respiratory insufficiency, chest pain, angina, etc.) present at the time of a scheduled vaccination, the vaccination can be delayed until symptoms subside, the underlying process is treated or resolves, or the subject may be withdrawn at the discretion of the Investigator. If vaccinations are delayed due to acute illness, timing for scheduled assessments and remaining vaccinations should be reestablished according to the original Schedule of Events ([Appendix 14.1](#)) as soon as possible.

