8.5 Assessment of Relationship to Study Drug (Causality)

Investigators are required to assess the causal relationship (i.e., whether there is reasonable possibility that the study drug caused the event) using the following definitions:

Unrelated: Another cause of the adverse event is more plausible; a temporal sequence cannot be established with the onset of the adverse event and administration of the investigational product; or, a causal relationship is considered biologically implausible.

Possibly Related: There is clinically plausible time sequence between onset of the adverse event and administration of the investigational product, but the adverse event could also be attributed to concurrent or underlying disease, or the use of other drugs or procedures. Possibly related should be used when the investigational product is one of several biologically plausible adverse event causes.

Definitely Related: The adverse event is clearly related to use of the investigational product.

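### Section 5.2.1 directs a stop after anaphylaxis only when it is definitely related, and gives no clear rule for a possibly related reaction

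*Protocol*

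**What the plan says.** Protocol 5.2.1 opens with a definition: "a dose-limiting toxicity (DLT) is defined as any anaphylactic reaction, a full-thickness ulceration/necrosis, or any AE" of Grade 3 or higher that is definitely related, with exceptions for short-lived injection reactions. It is unclear whether the causality qualifier at the end of that list also applies to anaphylaxis.

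Two instructions for the individual subject follow. The first is the stop: "Study drug should be discontinued for the subject in the case of a definitely related anaphylactic reaction or full-thickness ulceration/necrosis". The second concerns other related adverse events of Grade 3 or higher. After these, re-exposure "should only occur if the event resolved or is reduced to grade 1 toxicity".

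Section 8.5 sets three causality levels: unrelated, possibly related and definitely related. On the middle one it says: "Possibly related should be used when the investigational product is one of several biologically plausible adverse event causes". The top level requires a clear relationship.

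Three other sections bear on stopping treatment:
- Section 6.7: "Subjects who experience intolerable reactions will be discontinued from treatment but will remain on study".
- Section 8.7 removes a subject from treatment for intolerable toxicities that are due to PROSTVAC-V/F.
- Section 5.4 gives discretion. For the investigator: "the investigator may withdraw a subject if, in his/her clinical judgment, it is in the best interest of the subject". For the sponsor: "BNI may discontinue individual subjects, study arms, individual study centers, or the entire study at any time".

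**The concern.** The causality scale has a level meant for events with competing explanations, yet the one stop that names anaphylaxis applies only to the level above it. Competing explanations are foreseeable here. Exclusion criterion 17 leaves men with known or suspected contrast allergy eligible. Section 7.3 lists a contrast CT at Week 13, if clinically indicated, among the procedures done before that visit's vaccination; MRI is an option for men with contrast allergy. A reaction after both contrast and vaccine fits the possibly related definition, and vaccinations at Weeks 17 and 21 would still be due.

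Elsewhere the protocol uses a lower threshold. Section 8.15 requires follow-up of SAEs assessed as possibly or definitely related, and 8.12 uses the same pooling for SAEs that come to light after the study. Section 8.10 gives anaphylaxis as an example of an event where a single case is evidence of causation. That is reporting text and not a dosing rule, but it sits awkwardly beside a stop reserved for certainty.

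What is at stake is the safety of an individual man: a second exposure after a possible anaphylaxis can be life-threatening. No estimate or test in the trial depends on it.

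**Working it through.** The plan states no figure to reproduce. The check is to set the sections side by side for an anaphylactic reaction at each causality level.

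| Causality (8.5) | 5.2.1 | Other stops |
|---|---|---|
| Definitely related | Stop directed | 6.7, 8.7 and 5.4 also available |
| Possibly related | No rule (better reading), or no re-exposure before recovery (weaker reading, Grade 3 or higher only) | 6.7 if judged intolerable; 8.7 if judged intolerable and due to the vaccine; 5.4 by discretion |
| Unrelated | No stop | 6.7 if judged intolerable; 5.4 by discretion |

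**Which reading of 5.2.1 is better.** The re-exposure sentence covers *other* related events and comes directly after a sentence naming anaphylaxis and ulceration/necrosis. *Other* most naturally means event types apart from those two. Section 5.2.1 is then silent on a possibly related anaphylaxis. If *other* is taken to include it, the sentence sets a necessary condition for re-dosing. It is a restriction and does not grant permission, but it stops short of a prohibition.

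**Whether another section closes the gap.**
- Section 6.7 is mandatory and has no causality threshold, but its trigger is undefined and it does not name anaphylaxis. For discontinuation rules it refers the reader to 5.4 and not to 5.2.1.
- The nearest definition of intolerable is the Grade 3 row of Table 9-1 in 8.6, which applies only to events not listed in CTCAE. Reading every Grade 3 event as a mandatory stop would contradict the re-exposure sentence in 5.2.1.
- Section 8.7 again requires attribution to the vaccine, and does not mention GM-CSF.
- Section 5.4 says *may*.

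**Timing of the practical protections.** The shortest scheduled interval between vaccinations is 14 days (Weeks 1 to 3 and 3 to 5). With a 3-day window at both visits it is 14 − 3 − 3 = 8 days. SAEs are reportable within 24 hours whatever their causality (8.13, 8.14), so the sponsor would normally know of a serious reaction before the next vaccination. After a reaction at Week 1, 7 − 1 = 6 vaccinations remain; after Week 21, 7 − 7 = 0. Each needs a visit with adverse event questioning and an IVRS assignment first (7.3).

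The timing differs for home injections. Each cycle has four GM-CSF or placebo doses, the first given in clinic, so up to 4 − 1 = 3 may be at home outside France (6.5), the next perhaps due the following day. Section 6.3 has men return used and unused syringes, but does not link this to a reaction or tell them to stop injecting. The Pharmacy Manual was not available.

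**The case against.** The strongest answer is that Section 6.7 already deals with the case. It is mandatory, it does not depend on causality, and few clinicians would call anaphylaxis tolerable. Around it stand at least 30 minutes of clinic observation after each vaccination (6.4, 7.2, 7.3), SAE reporting within 24 hours, the sponsor's power to discontinue an individual subject, and side-effect education with study contact details in the home kit (6.6). A reaction with no competing cause would normally be graded definitely related, and the stop would apply. The threshold is also a design choice: lowering it removes some men whose reaction came from something else.

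Most of this stands. It makes actual re-dosing unlikely and keeps the point small. It does not supply a directed stop, because 6.7 still turns on an undefined judgement while the section that does name anaphylaxis limits its stop to definitely related cases.

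Four stronger inferences are tempting, and the documents do not support them:
- *The protocol permits re-dosing after a possibly related anaphylaxis.* It does not; the only sentence that might apply is a restriction.
- *The home syringes measure the gap.* The count is the same after a definitely related reaction, where the stop already applies.
- *The trial-level halt in 5.2.2 is part of the defect.* It counts "definitely related SAEs (per 20 patients) at any time after receiving study drug during the treatment period", but it governs dosing across the trial, not the individual man.
- *The ulceration/necrosis stop needs the same change.* The qualifier in the stop sentence may attach to anaphylaxis alone. Ulceration/necrosis would then already stop treatment whatever its cause, and adding a causality condition would weaken that protection.

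**Conclusion.** The point holds as a narrow gap in a safety rule. Section 5.2.1 directs a stop for definitely related anaphylaxis only; for a possibly related one no section that names the event directs a stop. The remaining protection rests on an undefined mandatory trigger in 6.7, an attribution-dependent one in 8.7, and discretion in 5.4.

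The size cannot be put as a number of men, because the documents give no anaphylaxis rate and no split by causality. For harm to follow, the reaction must be graded possibly related, not be treated as intolerable, and be followed by another dose without the investigator or sponsor stepping in. That is unlikely, but the consequence could be grave.

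Alpha, power, sample size and the ITT survival analysis are unaffected. This is a cheap improvement. The conclusion rests on the protocol text alone; the Pharmacy Manual or other site instructions may already say more about home syringes.

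**What to change.** Add to 5.2.1, in place of the anaphylaxis part of the present stop:

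> *Study medication (vaccine, GM-CSF or placebo) must be permanently discontinued after any anaphylactic reaction assessed as possibly or definitely related to study medication; the subject must be told at once not to use any remaining home syringes and to return them.*

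*Study medication* is the better term because 8.0 defines it to include GM-CSF and placebo, whereas *study drug*, used in 5.2.1, is not defined there. The instruction must be immediate because a home dose may be due the next day.

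Leave the existing ulceration/necrosis stop as worded, and leave the re-exposure sentence for other related events of Grade 3 or higher unchanged. Keep the open stops in 6.7 and 8.7 and add a cross-reference from each to 5.2.1. The discretion in 5.4 stays.

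The cost is one sentence, two cross-references and a short site instruction. A few men whose reaction had another cause would lose their remaining doses; they stay in follow-up and in the ITT analysis.
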